# **Health Education Model Led by Community Health Volunteers**

**NCT06312462**

**24-August-2025**

## **Study Protocol and Statistical Analysis Plan**

### **Study Design and Sampling**

A repeated cross-sectional design compared the impact of CHVs-led (CBPR-based) health education versus traditional health education on schistosomiasis-related KAP over 12 months (February 2024 - February 2025). The CBPR approach included: (1) Needs assessment using baseline surveys; (2) Co-design of interventions with community stakeholders; (3) Implementation led by trained CHVs; and (4) Mixed-methods evaluation combining infection rates and questionnaires(Figure 1). The process emphasized cultural adaptation, community ownership, and continued improvement to ensure sustainable interventions.

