### **Cluster Sampling Implementation**

A three-stage cluster sampling method was implemented:

1. School selection: Three public primary schools were randomly selected from distinct geographical regions of Pemba Island, matched for demographic characteristics (student population, gender ratio, and age distribution).
2. Cluster formation: Within each school, grades 4–6 (ages 8–16 years) were designated as natural clusters, reflecting the target population exposed to schistosomiasis transmission.
3. Participant inclusion: All students meeting eligibility criteria within selected grades were enrolled, minimizing selection bias through complete enumeration within clusters.

Intervention allocation:

- Intervention group: One school received CBPR-based education led by CHVs.

- Control group A and B: Two schools received standard health education from PHCs providers.

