## **Study design**

Baseline data were collected in February 2024, followed by a six-month intervention period. Post-intervention data were collected in August 2024, and a follow-up survey was conducted in February 2025 to assess the sustainability of the intervention effects. During the survey, face-to-face questionnaires were administered by CHVs to assess students' KAP related to schistosomiasis. Additionally, the research team distributed sterile wide-mouth plastic containers labeled with unique student identification numbers for morning urine sample collection. Each student provided approximately 30–50 mL of urine under teacher supervision to ensure proper collection procedures. The questionnaires, translated into Kiswahili, were pre-tested and validated. The questionnaire covered KAP of schistosomiasis transmission, exposure, and prevention. And include a survey on students' satisfaction with CHVs in the second questionnaire.

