## Statistical analysis

The data were double-entered into Microsoft Excel, systematically organized, coded, and verified for accuracy before being imported into IBM SPSS Statistics 26.0 for analysis. *S. haematobium* egg counts were stratified into light intensity (1–49 eggs/10 ml of urine) or heavy-intensity ( $\geq 50$  eggs/10 ml of urine) infection, based on WHO guidelines . For the KAP questionnaire: Knowledge scores were calculated based on correct responses (1 point per correct answer, maximum 10 points). Attitudes were evaluated using a 5-point Likert scale with a maximum score of 55 points. Behavioral patterns were scored according to frequency (1-3 points per item), totaling a maximum of 30 points. All scores were converted into percentage equivalents and categorized as "good" (80-100%), "moderate" (60-80%), or "poor" (<60%) . Satisfaction ratings were quantified with 1 point for "dissatisfied," 2 points for "neutral," and 3 points for "satisfied," yielding a maximum satisfaction score of 6 points.

Demographic and KAP data were analyzed descriptively: continuous variables were expressed as Mean  $\pm$  SD (normally distributed) or median [IQR] (non-normal). A two-way repeated-measures ANOVA with Bonferroni correction assessed temporal

effects (baseline/post-intervention/follow-up) and group differences. For ordinal data violating ANOVA assumptions (normality/homoscedasticity via Q-Q plots/Levene's test), the Kruskal-Wallis test was applied.

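### The fallback for the repeated-measures ANOVA is Kruskal-Wallis, an independent-samples test: if pupils are linked across waves it is conservative for change over time, and if it is used only between schools no such test remains for ordinal data

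*Combined protocol and SAP*

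**What the plan says.** The Statistical analysis section gives the main method: "A two-way repeated-measures ANOVA with Bonferroni correction assessed temporal" "effects (baseline/post-intervention/follow-up) and group differences". A repeated-measures ANOVA takes the waves as repeated observations on the same pupils.

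The same section gives the substitute. It opens "For ordinal data violating ANOVA assumptions", names Q-Q plots and Levene's test as the checks, and ends "the Kruskal-Wallis test was applied". It does not say whether Kruskal-Wallis compares waves, schools or both. It does not say which outcomes count as ordinal. No paired rank test and no ordinal model with a repeated unit is named.

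On linkage, the documents point in different directions:

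- Study Design and Sampling: "A repeated cross-sectional design compared the impact of CHVs-led" education with traditional education.
- Cluster Sampling Implementation: "All students meeting eligibility criteria within selected grades were enrolled", in three schools.
- Study design, on timing: a baseline in February 2024, then "Post-intervention data were collected in August 2024, and a follow-up survey was conducted in February 2025".
- Study design, on identifiers: urine containers were "labeled with unique student identification numbers for morning urine sample collection". Linking questionnaires by pupil is not described.

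**The concern.** A fallback should answer the same question as the test it replaces. The ANOVA addresses wave and group together and takes the within-pupil correlation into account. Kruskal-Wallis handles one factor, treats every observation as independent and has no group-by-wave term.

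The switch may not be rare. Attitude scores come from Likert items, behaviour scores from three-level frequency items, and all scores are also sorted into three categories. Any of these could be treated as ordinal and fail a normality check.

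At stake is the test of change over time for those outcomes. It may be run with an error variance that is too large, so that a modest real change is reported as non-significant, or it may not exist at all. The error is towards missing change, not towards false claims of change.

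**Working it through.** **Inputs.** From the documents: three waves, and a knowledge score of 0 to 10. Not in the documents, so assumed: alpha 0.05; 100 or 150 pupils in a within-school comparison; SD 2 points; exchangeable within-pupil correlation ρ from 0 to 0.8; the size of the shifts; no dropout. The plan gives no sample size, power or effect size, so there is no figure of its own to reproduce.

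**Step 1. What each reading of the text implies.**

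| Pupils linked? | Kruskal-Wallis compares | Consequence |
|---|---|---|
| Yes | Waves | Within-pupil correlation ignored; error variance too large |
| Yes | Schools only | No test of change over time for these data |
| No | Waves | Kruskal-Wallis is acceptable on this count, but the repeated-measures ANOVA does not fit |
| No | Schools only | No test of change over time, and the ANOVA does not fit |

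No row gives a main test and a fallback that both fit the data and both cover change over time.

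**Step 2. Type I error if pupils are linked and waves are compared.** With exchangeable correlation, the variance of differences between wave mean ranks shrinks by about the factor (1 − ρ). Kruskal-Wallis still divides by the independent-samples variance, so under no change its statistic behaves roughly as (1 − ρ) times a chi-square with 2 degrees of freedom. The 5% critical value is 5.991, hence

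P(reject) ≈ exp(−5.991 / [2(1 − ρ)]) = 0.05^(1/(1 − ρ)).

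- ρ = 0: 0.05^1 = 5%
- ρ = 0.3: 0.05^1.43 = 1.4%
- ρ = 0.5: 0.05^2 = 0.25%
- ρ = 0.7: 0.05^3.33 = 0.005%

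Simulation of a 0 to 10 score agrees in pattern. With 100 pupils the rates are 5.3%, 1.4%, 0.3% and about 0%. With 150 pupils they are 2.2%, 0.7% and 0.1% at ρ = 0.3, 0.5 and 0.7. Friedman stays at 4.4% to 5.6% (100 pupils, ρ from 0 to 0.8).

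**Step 3. Power for small shifts.** 150 pupils, shifts of 0, 0.2 and 0.15 SD at the three waves, three-wave omnibus test:

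| ρ | Kruskal-Wallis | Friedman | Loss in points | Loss as share of Friedman |
|---|---|---|---|---|
| 0.3 | 28% | 38% | 10 | 10/38 = 26% |
| 0.5 | 21% | 50% | 29 | 29/50 = 58% |
| 0.7 | 14% | 74% | 60 | 60/74 = 81% |

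**Step 4. Where the loss disappears.** At ρ = 0, with 100 pupils and a shift of 0.383 SD at both later waves, Kruskal-Wallis has 78% power and Friedman 71%, so nothing is lost. For a 0.5 SD shift with 100 pupils and ρ from 0.3 to 0.7, Kruskal-Wallis keeps 98% to 99%.

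**Step 5. Partial overlap.** If only two-thirds of pupils are repeated, the type I error of Kruskal-Wallis across waves is 3.0%, 1.5% and 0.3% at ρ = 0.3, 0.5 and 0.7. The test is therefore conservative even without full linkage.

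**The case against.** The strongest reply is that neither condition for a wrong error variance is written down. The design is called repeated cross-sectional. If each wave is a separate sample, Kruskal-Wallis across waves is sound on this count, the ANOVA is the mismatched test, and Friedman could not be run. Nor does the text say that Kruskal-Wallis compares waves. There are three schools, and Levene's test is a check between independent groups, both of which fit a between-school use. The trigger is ordinal data only, which might even mean the satisfaction items, asked only in the second questionnaire.

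Much of this stands, and it makes the point conditional. It does not remove it, because a between-school reading leaves no test of change over time, and a separate-samples reading sets the main test and its fallback on opposite assumptions.

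Three stronger readings are tempting and are not supported:

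- *The time test loses most of its power.* In these simulations that holds only for small shifts with a correlation of about 0.5 or more. The documents give neither quantity.
- *All scores that fail the checks go to Kruskal-Wallis.* The text limits the switch to ordinal data.
- *A decline from August to February would be missed and read as a sustained effect.* The power figures in Step 3 are for the omnibus test and rest mainly on the rise from baseline. The decline in that scenario is 0.20 − 0.15 = 0.05 SD, and a Bonferroni-adjusted Wilcoxon signed-rank test detects it in only 3.8%, 3.8% and 5.3% of runs at ρ = 0.3, 0.5 and 0.7. The documents state no expected decline from which to argue further.

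**Conclusion.** The point holds in conditional form. Kruskal-Wallis is not a like-for-like substitute for a two-way repeated-measures ANOVA, and the plan names nothing that is. If pupils are linked and waves are compared, the test is conservative. For small shifts, its power deficit against Friedman is about 10 points at correlation 0.3, 29 at 0.5 and 60 at 0.7. There is no deficit at correlation 0 and little for a 0.5 SD shift. If the test is used only between schools, change over time goes untested for these outcomes.

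The direction follows from the method. The sizes rest on assumed pupil numbers, shifts and correlations. Linkage itself is an open question in the documents: full enrolment of the target grades in the same three schools makes overlap likely, but that is an inference.

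**What to change.** 1. State whether pupils are linked across the three waves, fully or in part, and by what identifier on the questionnaire. Reconcile the repeated cross-sectional label in Study Design and Sampling with the repeated-measures ANOVA in Statistical analysis.
2. List the outcomes treated as ordinal and the waves at which each is measured.
3. For ordinal outcomes measured at more than one wave, replace Kruskal-Wallis with a cumulative-logit model, by GEE or with a random intercept. Use pupil as the repeated unit and include group, wave and group-by-wave terms. This also handles partly overlapping samples, provided that pupils seen more than once can be identified.
4. Where pupils are fully linked, a simple alternative is Friedman with Bonferroni-adjusted Wilcoxon signed-rank tests within each school. It covers change over time but not the group-by-wave comparison.
5. Keep Kruskal-Wallis only for comparisons of different pupils at a single wave.

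The cost is a few sentences of SAP wording and a re-run in SPSS 26, the software already named. No new data are needed if questionnaires carry the pupil identifier; if they do not, linkage cannot be recovered and that should be stated. The change deals with dependence between waves only. It does not address the delivery of the intervention in a single school.
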